4.4 Study periods, Baseline and Endpoint Values

- First date of medication administration

Day 1 date (collected in patients' V2-V5 diary) will be treated as first intake of study medication.

- Last date of medication administration

Day 28 date (collected in patients' V2-V5 diary) will be treated as last intake of study medication (if the subject completes the study this date should coincide with the date of last investigational product intake).

If the date of last intake of study medication is not available, due to premature termination or other reasons, date of last investigational product intake (collected in the end of study form of the CRF) will be imputed.

- Duration of study medication treatment

Duration (days) = Date of last medication administration - Date of first medication administration + 1

- Baseline value

The baseline value for a variable is defined as the last non-missing value collected before first study medication administration. In the single dose phase, the moment 0 (visit 1- hour 0) will be considered as baseline value while in the multidose phase, baseline will be visit 2 (day 0) if not specified otherwise.

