5.2 Efficacy Analysis

5.2.1 Primary Efficacy Analysis

The primary objective of this study is to evaluate the best dosage between 100mg once daily or 100mg twice daily for COQUN ORAL FORMULATION in order to reach a level of plasma concentration which might assure its antioxidant effect if taken on a regular basis.

The following pharmacokinetic properties will be evaluated:

- Area under the curve (microg/ml x h)
- C_{max}
- T_{max}
- Elimination half-life (t_{1/2})

Collected Variables

- Plasma concentration of coenzyme Q10 [CRF – Visit 2, 3, 4, 5]

	Form	Form No.	1M-DMST-011-01-A1
	Statistical Analysis Plan	Page	Page 21 of 69
		Effective Date	07/05/2018

Derived Variables

Derived variables are shown in Image 1 and are the following^[2,3]:

- AUC_t
The area under the plasma concentration curve to the last quantifiable concentration (C_t) at time t (AUC_t) will be determined by linear trapezoidal rule. The trapezoidal rule is a method used to numerically approximate the area under the concentration by time curve obtained by summing the area of all trapezoids constructed under the curve. Each trapezoid's area is obtained as:

$$\frac{(C_i + C_{i+1}) * (T_{i+1} - T_i)}{2}$$

where C_i is the concentration at time i (where i is any timepoint before the last observed timepoint T_t), C_{i+1} is the concentration at the following timepoint, T_i is the timepoint i and T_{i+1} is the following timepoint.

- C_{max}
Maximum concentration in the plasma (C_{max}) is obtained directly from the data being the highest plasma concentration value.
- T_{max}
 T_{max} is the collection time in which the maximum concentration is observed and is related to the drug absorption speed.
- $t_{\frac{1}{2}}$
The terminal half-life is defined as the time required for the plasma concentration of a drug to decrease 50% in the final stage of its elimination; this parameter is computed with the formula^[2]:

$$t_{\frac{1}{2}} = \frac{\ln 2}{\lambda_z}$$

where λ_z is the smallest elimination rate constant observed which is obtained as the ratio of clearance and volume of distribution. Clearance is calculated as the ratio of dose and AUC while volume of distribution is obtained as dose divided by concentration at time 0 that is the concentration registered after the first intake of coenzyme (in the single dose time 0 is hour 1, in the multidose phase time 0 is visit 2).

[figure not shown]

Image 1. Pharmacokinetic parameters

	Form	Form No.	1M-DMST-011-01-A1

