	Statistical Analysis Plan	Page	Page 22 of 69
		Effective Date	07/05/2018

Analysis of Primary Efficacy variable:

Descriptive statistics such as mean \pm standard deviation, median with interquartile range, minimum, maximum and coefficient of variation will be presented for the plasma concentration of coenzyme Q10 at each time point in the entire sample of subjects. 95% confidence interval will be provided as well.

An explorative analysis on gender will be performed showing descriptive statistics for plasma concentration of coenzyme Q10 by gender. The effect of gender will be explored by means of a mixed model for repeated measures with covariates *gender*, time and the interaction term *gender*time*.

Descriptive statistics will be also provided for the plasma concentration of coenzyme Q10 at each time point by treatment group.

Change of plasma concentration versus baseline (i.e. change versus visit 2 values) will be computed for each study visit both for the whole sample and by treatment group.

Change will be computed in the following way:

$$\text{Change (\%)} = \frac{\text{Value at Visit X} - \text{Baseline Value}}{\text{Baseline Value}} \times 100$$

Area under the curve, maximum concentration in the plasma, time of maximum concentration and terminal half-life will be presented descriptively on the original scale.

95% confidence interval will be provided for the means of 100mg OD and 100mg BID for COQUN ORAL FORMULATION for the parameters AUC_t , C_{max} , T_{max} and terminal half-life. A Student t-test for unpaired data will be performed in order to detect differences between the two groups in the pharmacokinetics parameters.

A concentration by time graph will be presented for the multidose phase by treatment group in order to have a graphical visualization of the pharmacokinetics properties over time.

Line graphs will be provided for the concentration of coenzyme Q10 in the whole sample and by gender.

In performing statistical analysis, it is important to assess the statistical outliers. In fact, inclusion or exclusion of outlying subjects may lead to a different conclusion in assessment of differences in bioavailability between two formulations. It is therefore important to identify these outliers and study their effects.

Primary endpoint will be evaluated on the ITT population and analysis will be replied on the PP population. Results obtained on the PP population will be considered as supportive of those obtained on the ITT set.

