5.2.3 Analysis of Other Variables

An analysis of the bioavailability evaluated in the first single dose phase of the study will be performed.

The following pharmacokinetic properties will be evaluated:

- Area under the curve (microg/ml x h) ≥ 5
- C_{max} (microg/ml x h) $\geq 0,8$
- T_{max} (hours) ≥ 3
- Elimination half-life ($t_{\frac{1}{2}}$)

The plasma concentration is recorded at Visit 1 at moment 0 (before COQUN intake), hour 1, hour 2, hour 4, hour 8 and hour 12.

Collected Variables

- Plasma concentration of coenzyme Q10 [CRF – Visit 1]

Derived Variables

The parameters AUC_t , AUC_{∞} , C_{max} , T_{max} , $t_{\frac{1}{2}}$ and their computation have been described in section 5.2.1 Primary Efficacy Analysis. Please refers to the mentioned section for details.

Analysis of Primary Efficacy variable:

Descriptive statistics such as mean \pm standard deviation, median with interquartile range, minimum, maximum and coefficient of variation will be presented for the plasma concentration of coenzyme Q10 at each time point in the entire sample of subjects. 95% confidence interval will be provided as well.

An explorative analysis on gender will be performed showing descriptive statistics for plasma concentration of coenzyme Q10 divided by gender. The effect of gender will be explored by means of a mixed model for repeated measures with covariates *gender*, time and the interaction term *gender*time*.

	Form	Form No.	1M-DMST-011-01-A1
	Statistical Analysis Plan	Page	Page 28 of 69
		Effective Date	07/05/2018

Change of plasma concentration versus baseline (i.e. change versus hour 0 values) will be computed for each study visit both for the whole sample and by gender. Change will be computed in the following way:

$$\text{Change (\%)} = \frac{\text{Value at Visit X} - \text{Baseline Value}}{\text{Baseline Value}} \times 100$$

Area under the curve, maximum concentration in the plasma, time of maximum concentration and terminal half-life and half-life will be presented descriptively on the original scale.

95% confidence interval will be provided for the means of the parameters AUC_t , C_{max} and T_{max} and terminal half life in the single dose phase i.e. following a single intake of COQUN oral formulation.

A concentration by time graph will be presented for the single dose phase in order to have a graphical visualization of the pharmacokinetics properties over time.

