5.3 Pharmacokinetic (PK)/ Pharmacodynamic (PD)

Pharmacokinetic properties evaluated for this study are the following:

- Area under the curve (AUC_t)
- Maximum concentration in the plasma (C_{max})
- Time taken to reach the maximum concentration (T_{max})
- Elimination half-life ($t_{1/2}$)

The detailed description of the analysis of pharmacokinetic variables is provided in section 5.2.1 Primary efficacy analysis.

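### The SAP's half-life formula reduces to ln 2 × AUC/C0: it estimates no rate of decline, and in the multidose phase it lengthens when plasma levels rise above Visit 2, even if elimination is identical

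*SAP*

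**What the plan says.** SAP 5.2.1 (Derived Variables) defines the terminal half-life as the time for the concentration to "decrease 50% in the final stage of its elimination" and sets t½ = ln 2/λz, with λz the ratio of clearance to volume of distribution. It continues: "Clearance is calculated as the ratio of dose and AUC while volume of distribution is obtained as dose divided by concentration at time 0". Time 0 is then fixed: "in the single dose time 0 is hour 1, in the multidose phase time 0 is visit 2". AUC_t is the linear trapezoid to the last quantifiable concentration. The visible text describes no regression on terminal points.

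For the multidose phase, SAP 5.2.1 adds: "A Student t-test for unpaired data will be performed in order to detect differences between the two groups in the pharmacokinetics parameters". The Table 17 shell has a t½ row, and its note treats p below 0.05 as statistically significant.

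For the single-dose phase, SAP 5.2.3 plans a 95% interval for "terminal half life in the single dose phase i.e. following a single intake of COQUN oral formulation". It lists the parameters, including AUC to infinity, "and their computation have been described in section 5.2.1 Primary Efficacy Analysis". SAP 5.3 also refers back: "The detailed description of the analysis of pharmacokinetic variables is provided in section 5.2.1 Primary efficacy analysis".

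Protocol 7.2 and 12.7 list t½ among the primary variables. Listings 17 and 25 also print clearance and volume.

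**The concern.** The definition concerns the final stage of elimination, but the formula uses no slope. Samples after the peak enter only through the area.

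C0 is unsuitable in both phases:

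- **Single dose.** C0 is the hour-1 sample, taken before the Tmax of at least 3 h that the plan targets, while drug is still being absorbed.
- **Multidose.** C0 is Visit 2, and SAP 4.4 says that "in the multidose phase, baseline will be visit 2 (day 0) if not specified otherwise". All later samples (Days 7, 14 and 28) fall during continued dosing, so no elimination phase is observed.

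At stake is a false statement about elimination in the study report. If BID raises levels more than OD, as the protocol expects, the t-test on t½ can report that elimination differs by regimen when only exposure differs.

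**Working it through.** **1. Algebra.** CL = dose/AUC and V = dose/C0, so λz = CL/V = C0/AUC and t½ = ln 2 × AUC/C0. Dose cancels if the same dose is used in both. As a check, a multidose profile of 0.8/1.5/2.0/2.5 µg/ml returns 1077.15 h for dose inputs of 100, 200, 2800 and 5600 mg.

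**2. Where the formula is right.** For a mono-exponential intravenous bolus with AUC to infinity and no baseline, true half-lives of 4, 12 and 33 h are recovered exactly. None of those conditions holds here.

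**3. Flat profile, no elimination information.** Single dose (0 to 12 h): ln 2 × 12 = 8.3 h. Multidose (0 to 28 days = 672 h): ln 2 × 672 = 466 h = 19.4 days.

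**4. Single dose.** Sampling times 0, 1, 2, 4, 8 and 12 h are from the plan. The rest is assumed: a one-compartment oral profile on a constant baseline of 0.4, 0.8 or 1.2 µg/ml; peak increment 0.6; ka 0.15, 0.3, 0.6, 1 or 2 per h; true t½ 6, 12, 33 or 96 h (60 scenarios).

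- Over all 60 scenarios the formula returns 6.6 to 12.9 h.
- In the 45 scenarios with true Tmax of at least 3 h it returns 8.5 to 12.9 h.
- At baseline 0.8, raising the true half-life from 6 to 96 h (16-fold) moves the result from 7.1 to 8.5 h at ka 2, and leaves it at 10.7 h at ka 0.15.

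**5. Multidose.** Days 0, 7, 14 and 28 are from the SAP; 2.5 (OD) and 3.5 (BID) µg/ml are the literature levels in protocol 6.1. Baseline 0.8 is assumed. With the plateau reached by Day 7:

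- OD: AUC = 7 × (0.8 + 2.5)/2 + 21 × 2.5 = 64.05; t½ = 0.6931 × 64.05/0.8 = 55.5 days.
- BID: AUC = 7 × (0.8 + 3.5)/2 + 21 × 3.5 = 88.55; t½ = 0.6931 × 88.55/0.8 = 76.7 days.

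| Levels (µg/ml), baseline 0.8 | Pattern | OD (days) | BID (days) |
|---|---|---|---|
| 2.5 / 3.5 | plateau by Day 7 | 55.5 | 76.7 |
| 2.5 / 3.5 | 50% and 75% of the rise at Days 7 and 14 | 46.5 | 62.4 |
| 1.5 / 2.0 (assumed) | plateau by Day 7 | 34.3 | 44.9 |

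Over baselines 0.4 to 1.2 and both patterns, the BID/OD ratio is 1.32 to 1.39 at 2.5/3.5, and 1.23 to 1.32 at 1.5/2.0. A dosing model with the same true half-life of 33 h in both arms (assumed ka 0.3 per h, baseline 0.8) returns 776 h for OD and 1045 h for BID.

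**6. The planned t-test.** Simulation with 12 per arm, log-normal concentrations, mean Visit 2 level 0.8, final means 2.5 and 3.5, and correlations between Visit 2 and later visits of 0 to 0.8. The test gives p < 0.05 in 72–100% of trials at CV 20%, 39–100% at CV 30% and 16–88% at CV 50%. With equal levels in both arms it gives 4–5%. The rejections therefore come from the exposure difference.

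**7. Reading AUC as AUC to infinity.** The visible text of 5.2.1 gives no extrapolation rule. With the usual one, AUC_inf = AUC_t + C_last/λz and λz = C0/AUC_inf, so AUC_inf = AUC_t/(1 − C_last/C0). This has no valid value when C_last is at or above C0. That happens in 42 of the 60 single-dose scenarios, and for any multidose subject whose Visit 5 level is at or above Visit 2.

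**The case against.** The strongest objection is about consequence. The study is exploratory, protocol 12.6 pre-specifies no hypotheses, t½ has no threshold, and no dose criterion uses it. The primary objective concerns plasma level, which AUC_t, Cmax and Tmax address without this formula. All of that stands, and it limits the harm. It does not justify printing, with an interval and a p-value, a primary variable that does not measure what the SAP defines.

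Other points, and what remains of them:

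- **Visit 2 might be post-dose.** SAP 5.2.1 describes C0 as measured after the first intake, and the flow chart marks intake at V2. But SAP 4.4 makes Visit 2 the baseline and takes the Day 1 diary date as first intake. Visit samples are fasting (protocol 10.6.9 and 10.6.16) and doses follow lunch or dinner (9.4). The pre-dose reading is the better one.
- **Only a rise relative to Visit 2 matters.** Correct: if all four values scale together, the result does not change.
- **Clearance contains no C0.** Correct. Volume inherits the C0 problem. Clearance fails because its AUC is truncated and includes the endogenous level, and because the SAP does not say whether the multidose dose is per intake, daily or cumulative.
- **Image 1 is not shown.** It could hold an AUC-to-infinity rule. The extrapolation in step 7 is the usual one, not one stated in the SAP.
- **The sizes rest on assumptions.** The documents give no adult baseline, absorption rate or variability. Baselines of 0.2 and 0.1 raise the single-dose maximum to 15.8 and 19.3 h. The algebra and the flat-profile results need none of these inputs.

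**Conclusion.** The concern holds. The reduction to ln 2 × AUC/C0 is exact and contradicts the definition in the same bullet. In the single-dose phase the result is nearly insensitive to true elimination at a fixed absorption rate and baseline (at most about a 20% change for a 16-fold change in half-life at baseline 0.8). In the multidose phase it is a measure of exposure relative to baseline. At the protocol's own literature levels it gives BID a value about a third longer than OD with the same elimination.

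The direction depends only on BID levels rising further above Visit 2 than OD levels. The days, ratios and rejection rates depend on the stated assumptions; the simulation shows that the test can reject and does not predict this trial. The damage is confined to statements about half-life, clearance and volume. It does not reach the choice of regimen.

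**What to change.** Before database lock, amend the SAP as follows.

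- **5.2.1:** delete the clearance/volume route to λz.
- **Multidose:** remove t½, clearance and volume from the 5.2.1 parameter list, Tables 16 and 17 and Listing 17. Remove the t½ interval and t-test from the text, and state that no elimination phase is sampled.
- **Single dose:** remove t½, clearance and volume from 5.2.3, Table 28 and Listing 25, stating that sampling to 12 h does not support a terminal half-life. Delete the AUC-to-infinity mention, which has no row in Table 28.
- **If a single-dose t½ is kept:** label it exploratory. Use only strictly post-peak, declining points after subtracting the Visit 1 hour-0 value, and state the minimum number of points in advance. Otherwise report it as not estimable, give the number of subjects with an estimate, and run no between-group test. State that a sampled Tmax of 4 h or later leaves at most two points, and that continuing absorption biases the estimate upward: at ka 0.3 per h, a slope from 8 to 12 h returns 8.7 h for a true 6 h.
- **5.3 and section 6:** amend 5.3 to match and record the change in section 6, which now declares none. A note against the protocol's t½ entries (synopsis, 7.2, 10.3, 10.5.1, 12.7), or in the study report, is enough; protocol 12.1 already provides for reporting deviations.

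The cost is SAP wording, table and listing shells, and programming. A listed primary variable becomes unavailable in the multidose phase. In the single-dose phase it is unavailable if dropped, and only partly available if the exploratory version is kept: two or more post-peak samples exist in 11 of the 20 modelled ka and half-life pairs, and in 6 of the 15 with true Tmax of at least 3 h.

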2.3 Randomization

After the screening visit, subjects will have one week of wash-out period, then will be requested to return to the site for V2, during which subjects will be randomly assigned to one of the two groups:

- group A: 12 adult healthy subjects will be given OD 100mg of COQUN ORAL FORMULATION, to be taken after dinner
- group B: 12 adult healthy subjects will be given BID a dose of 100 mg of COQUN ORAL FORMULATION, to be taken after lunch and after dinner

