3.2 Subgroups

No subgroup analysis has been planned in this study.

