Imputations for missing values: No imputation of missing data will be performed

Analysis Sets to be used for:	Tables	ITT and PP analysis set
	Listings	ITT analysis set
	Figures	ITT and PP analysis set

	Form	Form No.	1M-DMST-011-01-A1
	Statistical Analysis Plan	Page	Page 23 of 69
		Effective Date	07/05/2018

Primary efficacy variable will be summarized by treatment group as follows:

Table 13. Primary Efficacy Variable at Each Study Visit (ITT Analysis Set)

Default summary statistics per treatment group for the primary efficacy variable (Plasma concentration of Coenzyme Q10) at each study visit will be presented for the ITT analysis set.

This table will be replied on the PP analysis set.

Table 14. Plasma concentration of coenzyme Q10 by gender (ITT Analysis Set)

Default summary statistics per gender for the primary efficacy variable (Plasma concentration of Coenzyme Q10) at each study visit will be presented for the ITT analysis set.

This table will be replied on the PP analysis set.

Table 15. Change versus baseline by Treatment (ITT Analysis Set)

Default summary statistics per treatment group for the change versus baseline at each study visit will be presented for the ITT analysis set.

This table will be replied on the PP analysis set.

Table 16. Pharmacokinetic Parameters by Treatment (ITT Analysis Set)

Default summary statistics per treatment group for each pharmacokinetic parameter will be presented for the ITT analysis set.

This table will be replied on the PP analysis set.

Table 17. Confidence Interval and Results of T-test for Primary Efficacy Variable (ITT Analysis Set)

Confidence interval at 95% will be presented for the means of the pharmacokinetics parameters in the two groups in the ITT analysis set. The table also contains the result of the Student t-test detecting the differences between the two groups.

This table will be replied on the PP analysis set.

A Primary efficacy variable will be presented in subject data listings as follows:

Listing 16. Listing of Primary Efficacy Variable

A listing of the values for the primary efficacy variable (Plasma concentration of Coenzyme Q10) as used in the primary analysis, sorted by screening number and within subjects by time point will be presented.

Listing 17. Listing of Pharmacokinetic parameters

A listing of the values for the pharmacokinetic parameters as used in the primary analysis, sorted by screening number will be presented.

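### The exploratory multidose gender model in SAP 5.2.1 omits the randomised arm, which costs precision and leaves the gender estimates open to chance gender-by-dose imbalance

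*SAP*

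**What the plan says.** SAP 5.2.1 describes the multidose gender analysis in two steps. The first is descriptive: "An explorative analysis on gender will be performed showing descriptive statistics for plasma concentration of coenzyme Q10 by gender". The second is a model: "The effect of gender will be explored by means of a mixed model for repeated measures with covariates" gender, time and gender*time. Neither treatment nor treatment*time appears, and nothing elsewhere in the SAP or protocol adds them.

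The data for this section are given as "Plasma concentration of coenzyme Q10 [CRF – Visit 2, 3, 4, 5", that is, V2 (the multidose baseline) and three visits on treatment. The gender displays pool the arms in the same way. Table 14 is specified as "Default summary statistics per gender for the primary efficacy variable (Plasma concentration of Coenzyme Q10) at each study visit", and Figure 5 plots concentration by gender only.

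On allocation, SAP 2.3 says that subjects return for V2, "during which subjects will be randomly assigned to one of the two groups", with 12 per group. Neither SAP 2.3 nor Protocol 9.6 describes stratification by gender. SAP 3.2 states: "No subgroup analysis has been planned in this study".

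SAP 5.2.3 uses the same gender model for the single-dose phase, where all subjects take the same 100 mg dose.

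**The concern.** The wording that suits the single-dose phase is carried into a phase where subjects receive two different daily doses. Protocol 6.1 and 6.2 cite literature levels of about 2.5 µg/ml for 100 mg once daily and about 3.5 µg/ml for 100 mg twice daily. If anything like that difference occurs in this study, the model leaves out a known factor that moves the outcome by about 1.0 µg/ml.

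Two things follow. The dose difference goes into the unexplained variation, so the gender effect is estimated less precisely than the data allow. And if men and women happen to split unevenly between OD and BID, part of the dose difference appears in the gender estimate of that trial. Because V2 precedes multidose intake, dose can act only at V3, V4 and V5, so gender*time is exposed as well as the gender main effect.

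**Working it through.** The SAP gives no power, precision or covariance figure for this model, so there is no stated figure to reproduce. The check is a single-visit approximation.

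**Inputs**
- 24 subjects, 12 per arm: SAP 2.5.
- Dose difference D = 3.5 − 2.5 = 1.0 µg/ml: literature levels in Protocol 6.1 and 6.2, taken as an assumption for this product.
- Gender split: not in the documents. Assumed 12 men and 12 women, with 8 women/16 men and 6 women/18 men as the range.
- Within-arm SD: not in the documents. Assumed range 0.3 to 1.5 µg/ml.
- Two-sided 5% level for the gender test: assumed. The SAP states 0.05 only for the t-tests of Table 17.

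**Step 1: chance imbalance.** With unstratified 12:12 allocation and 12 of each gender, the number of women on BID is hypergeometric: P(k) = C(12,k)² / C(24,12).
- P(6) = 0.316, exact balance.
- P(5) = P(7) = 0.232.
- P(4) = P(8) = 0.091.
- P(8:4 or worse) = 0.220.

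**Step 2: shift in the gender contrast.** Shift = D × (share of women on BID − share of men on BID).
- 7:5 split: 1.0 × (7/12 − 5/12) = 0.17 µg/ml.
- 8:4 split: 1.0 × (8/12 − 4/12) = 0.33 µg/ml.
- Over all allocations the mean shift is exactly 0, the mean absolute shift 0.16 and the SD 0.21 µg/ml.
- With 8 women/16 men, P(|shift| ≥ 0.33) = 0.19; with 6/18 it is 0.16. The mean shift is 0 in both.

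These values apply to one post-baseline visit. If the full 1.0 difference is present at V3, V4 and V5 and absent at V2, the four-visit average difference is (0 + 1 + 1 + 1)/4 = 0.75. The 8:4 shift in the averaged gender contrast is then 0.75 × 0.33 = 0.25 µg/ml. The change in the contrast from V2 to a later visit, which gender*time describes, carries the full 0.33.

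**Step 3: standard error.** Omitting dose adds D²/4 = 0.25 (µg/ml)² to the variance, so the SE ratio is √(1 + D²/(4 SD²)).

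| Within-arm SD (assumed, µg/ml) | SE ratio, formula | Simulated SE without → with treatment | Power for an assumed 0.75 µg/ml gender difference, without → with |
|---|---|---|---|
| 0.3 | 1.94 | not run | not run |
| 0.5 | 1.41 | 0.290 → 0.207 | 0.69 → 0.93 |
| 0.75 | 1.20 | 0.366 → 0.310 | 0.49 → 0.63 |
| 1.0 | 1.12 | 0.454 → 0.413 | 0.35 → 0.41 |
| 1.5 | 1.05 | 0.640 → 0.620 | 0.203 → 0.207 |

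The simulations used 6,000 randomised trials per setting with 12 women and 12 men. Type I error was 0.044 to 0.056 with or without the treatment term, over these runs and matching ones with 8 women.

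**Step 4: steps 2 and 3 describe the same variation.** At SD 0.5, combining the adjusted SE with the SD of the chance shift gives √(0.207² + 0.21²) = 0.295, close to the unadjusted SE of 0.290. The larger SE is the price of the chance shift, not an addition to it.

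**Step 5: the 5% error rate is an average over splits.** With no true gender effect, the false-positive rate of the unadjusted single-visit test given the realised split (40,000 simulated trials each) is:
- SD 0.5: about 0.5% at 6:6, 12% at 8:4, 38% at 9:3.
- SD 1.0: about 3% at 6:6, 8% at 8:4, 16% at 9:3.

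**The case against.** A reader might infer that the gender effect is confounded with dose. The documents do not support that. Arm is assigned at random at V2, independently of gender, so the estimate is unbiased over allocations and the test keeps its nominal size on average. A reader might also count the 0.33 µg/ml shift and the inflated SE as two separate harms; step 4 shows that they are largely one.

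The sizes are also conditional. The 2.5 and 3.5 µg/ml levels are literature values for a well-absorbed supplement taken over time, and Protocol 6.1 says that levels depend on the formulation. They are not predictions for this product. At a within-arm SD of 1.5 the loss is negligible. The absence of stratification is only an absence of description, since no randomisation method is given.

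The plan offers some protection. The Table 5 shell shows gender by arm, so an imbalance would be visible; Table 13 gives concentrations by arm; and no listed table has a place for the model's estimate or p-value. The wording of SAP 3.2 can be read as ruling out only treatment comparisons within subgroups, which a gender main-effect model is not.

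All of this lowers the severity. It does not remove the point. Only one allocation will be realised, and step 5 shows that the error rate given that allocation can lie well below or above 5%. Seeing an imbalance in Table 5 does not adjust for it.

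**Conclusion.** The point holds as a minor one. The multidose gender model omits a randomised factor that is expected to affect the outcome, which costs precision and leaves the realised gender and gender*time estimates open to chance imbalance. With D = 1.0 µg/ml and 12 of each gender, there is a 22% chance of an 8:4 or worse split; at 8:4 the shift is about 0.33 µg/ml at a post-baseline visit and about 0.25 averaged over V2-V5. The corresponding SE inflation runs from about 94% (SD 0.3) to about 5% (SD 1.5). Its actual size is unknown because the documents give no within-arm SD.

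There is no systematic bias and no average inflation of the type I error. The analysis is labelled explorative, and the OD versus BID comparison in the same section does not depend on it. Severity is low.

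**What to change.** In SAP 5.2.1, add treatment and treatment*time as fixed effects to the multidose gender model. Both are needed, because dose cannot act at V2 and can act from V3 onwards. With four visits this uses 1 + 3 = 4 fixed-effect degrees of freedom. It needs one line of SAP text and model code, and no new data. Leave the single-dose model in SAP 5.2.3 unchanged.

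Showing Table 14 and Figure 5 by gender within arm is optional, since an even split leaves about 6 subjects per cell. SAP 3.2 could note, as a minor clarification, that exploratory gender analyses are planned in both phases.
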